Methodology: Subjects will be patched with a test material, a positive control and a negative control 10 times over 40 days, 9 during Induction Phase and 1 during Challenge Phase. Each patch will be worn for approximately two days. Before each patch application, the test site will be evaluated using the Erythemal Scoring Scale (ESS) and Additional Reaction Scoring. Following a Rest Phase of approximately 10 to 14 days, the subjects will again be patched on a virgin test site with the test material (but not the negative control nor the positive control). After two days of skin contact, the test sites will be evaluated using the ESS and Additional Reaction Scoring on removal day and Days 1 and 2 post-removal. The ESS and Additional Reaction Scoring results will be evaluated to determine the allergic potential of the test material. The three test sites will be as follows: test material; saline negative control; and positive control (0.4% SLS).

Number of Subjects Planned and Analyzed: Approximately 57 subjects will be enrolled in the trial so that at least 50 subjects will complete the trial. Data from all subjects who complete the Induction Phase will be analyzed for irritant contact dermatitis potential. Data from all subjects who complete the Challenge Phase will! be analyzed for allergic contact sensitization potential.

[figure not shown]
Diagnosis and Main Criteria for Inclusion: Healthy adult male and non-pregnant females aged 18-79 years, inclusive.

Test Material, Dose and Mode of Administration, Batch Number: The test material, approximate 8 mm disc of NeoMatriX™, will be applied to the cotton pad of each patch. Patches consisting of the test material and controls will be applied to specific test sites on the back of each subject.

Duration of Treatment: Fresh patches of test material and controls during the Induction Phase (approximately 3 weeks); no patches during the Rest Phase (approximately 2 weeks); and one patch of test material during Challenge Phase (approximately 1 week). No negative control nor positive control will be applied during the Challenge Phase.

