Criteria for Evaluation: Irritant contact dermatitis potential and allergic contact sensitization potential will be assessed through the evaluation of the test sites of application using the ESS and Additional Reaction Scoring. Statistical Methods: The ESS scores and Additional Reaction Scoring scores will be tabulated. The incidence of AEs, new-onset AEs, will be summarized. Maximum intensity and duration of AEs will be summarized by treatment group.

FLOW CHART OF TRIAL DESIGN

1 Background

A repeated insult patch test is a test devised to ascertain if an agent has the potential to cause contact irritation or contact allergy in the skin (Reference 12.1 and 12.2). Allergy is only elicited in immunologically competent individuals who have become sensitized through exposure to the agent following repeated cutaneous patch applications.

2 Trial Objective

The first primary objective of this trial is to determine by repetitive epidermal contact, the primary or cumulative irritation potential of a test material.

The second primary objective of this trial is to determine by repetitive epidermal contact, the allergic contact sensitization potential of a test material.

3 Proposed Schedule

Proposed trial initiation and termination dates will be established prior to the start of testing. The summary schedule of Induction Phase visits is shown in the table below.

[figure not shown]
Induction Phase Visits

The summary schedule of Rest Phase and Challenge Phase visits is shown in the table below.

K

, 3

Rest Phase and Challenge Phase Visits

4 Test Materials

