5.4 Withdrawal of Subjects

The subject is free to withdraw their consent to participate in the trial at any time and for any reason, in accordance with the principles of the World Medical Association Declaration of Helsinki (as amended) and of the Belmont Report. The PI also has the right to withdraw a subject from the trial for safety, lack of efficacy or administrative reasons.

Possible reasons why a subject may be withdrawn from the trial include the following:

- 1. Experiences a serious or intolerable AE;
- 2. Develops, during the course of the trial, symptoms or conditions listed in the exclusion criteria, including pregnancy;
- 3. Takes medications that are contraindicated, as described in the exclusion criteria;
- 4. Incurs a protocol violation such as failure to comply with the specified treatment regimen or failure to comply with the visit schedule; or
- 5. Requests an early discontinuation due to:
 - A clinical reaction for which the PI did not consider removal from the trial to be necessary;
 - Other (non-specific) subject-initiated reason

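### A suspected reactor who leaves because of a skin reaction before completing Challenge is recorded as an adverse event but has no stated place in the sensitization result.

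*Combined protocol and SAP*

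**What the plan says.** The analysis sets are defined in the synopsis, under Number of Subjects Planned and Analyzed. Irritation: "Data from all subjects who complete the Induction Phase will be analyzed for irritant contact dermatitis potential". Sensitization: "Data from all subjects who complete the Challenge Phase". The same entry gives the size: "Approximately 57 subjects will be enrolled in the trial so that at least 50 subjects will complete the trial". The Methodology entry has subjects patched "10 times over 40 days, 9 during Induction Phase and 1 during Challenge Phase". Section 6.1 (Design) ties sensitization to the readings at Challenge patch removal and on the next two days.

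Section 5.4 (Withdrawal of Subjects) says: "The PI also has the right to withdraw a subject from the trial for safety, lack of efficacy or administrative reasons". Its list of reasons includes "Experiences a serious or intolerable AE" and a subject's own request to stop because of "A clinical reaction for which the PI did not consider removal from the trial to be necessary". Sections 6.4.1 and 6.4.2 make any erythema or additional-reaction severity score of 2 to 4 an adverse event. Section 8.4 allows application to be interrupted or stopped, and requires it to stop when the cause of a serious or potentially serious event is in doubt.

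For withdrawn subjects, section 5.5 calls for the date and reason to be recorded and for the final-visit evaluations to be done. Section 8 calls for follow-up to outcome and a written summary when the cause is an adverse event. The synopsis says that scores will be tabulated, without saying for whom, and section 7 foresees no statistical methods.

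**The concern.** Leaving the trial can be a consequence of the very thing being measured. Section 1 (Background) says that allergy is elicited in people "who have become sensitized through exposure to the agent following repeated cutaneous patch applications", so a reaction late in Induction could be allergic; the protocol does not say how often. A subject who leaves at that point never receives the Challenge patch on a new site and does not meet the sensitization set. A subject who leaves during Induction also fails the Induction-completer definition used for irritation.

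The output of this test is a count that may be very small or zero, so one subject can change the message. At stake is a statement that no sensitization was seen among completers, made without reference to someone who left because the test site reacted.

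**Working it through.** **1. Follow a suspected reactor through the visible text, by time of exit.**

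| Exit for a test-site reaction | Adverse event and withdrawal record | Challenge-completer set |
|---|---|---|
| During Induction | Yes, if the score is 2 to 4 | Out |
| During Rest | Yes, if the score is 2 to 4 | Out |
| After the Challenge patch, before the last reading | Yes, if the score is 2 to 4 | Out, although some readings may exist |
| None: all Challenge readings completed | Yes, if the score is 2 to 4 | In |

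The final-visit evaluations in section 5.5 cannot stand in for a Challenge patch that was never applied. Re-Challenge (section 6.3.3) is triggered only by a reaction during Challenge. No visible text moves the first three rows into the sensitization result.

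**2. Direction.** With x reactors among n completers, adding one omitted true reactor changes the proportion by (x+1)/(n+1) - x/n = (n - x)/[n(n+1)], which is never negative. Omitting a true reactor therefore cannot raise the result. If the omitted reaction was irritant, no sensitized subject has been lost.

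**3. How many subjects could be affected.** The plan's enrolment figure cannot be derived, because no dropout rate is stated. It is consistent with one of about 12%: 50/(1 - 0.12) = 56.8, rounded up to 57. The allowance is 57 - 50 = 7 subjects, or 7/57 = 12.3%, and it covers every cause of leaving. The reaction-related share lies anywhere from 0 to all 7 when exactly 50 of 57 complete.

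**4. Schedule.** Of 10 patches, 9 (90%) come before Challenge. With 21 days of Induction (section 6.1) and 10 to 14 days of Rest (synopsis), the Challenge patch goes on at about day 21 + 10 = 31 to 21 + 14 = 35 of 40. Most exposure precedes the readings used for sensitization. This describes the timetable and is not a risk of leaving because of a reaction.

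**5. Illustration.** Assume that 50 complete, none reacts, and k of the 7 non-completers left as true reactors. Limits are exact (Clopper-Pearson), two-sided 95%.

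| Result | Proportion | 95% limits |
|---|---|---|
| Completers, 0/50 | 0% | 0 to 7.1%, from 1 - 0.025^(1/50) |
| All enrolled, k = 1: 1/57 | 1.8% | 0.04 to 9.4% |
| All enrolled, k = 7: 7/57 | 12.3% | 5.1 to 23.7% |

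The counts are assumed, and k = 7 requires every non-completer to be a true reactor. The table shows that one omitted subject turns a zero into a non-zero finding. It does not estimate the bias in this trial.

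**The case against.** The strongest objection is that the operative text is not available. In this copy, sections 6.3 and 6.3.2 are headings without text, no Induction procedure appears, and the scoring scales are absent. A rule for strong reactors would normally sit there: move the site, stop Induction patching but still challenge, or count the subject as presumptive. This stands. A reader might infer that the protocol has no rule for reactors, and the documents do not support that. The point rests on the visible analysis-set sentence, which refers to no such rule.

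A reader might also infer that the reaction disappears from the trial. It does not. Scores of 2 to 4 become adverse events, relationship to test material is graded (section 8.1), the withdrawal reason is recorded, and the synopsis promises a summary of adverse events. The gap is that none of this is linked to the sensitization result.

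Nor does stopping application under section 8.4 mean leaving the trial. Nothing visible bars a subject whose Induction patching was stopped from being challenged on a new site, and a subject who then completes Challenge is counted. Challenge itself has one patch, so its later readings need no further application. The exposure to this problem is therefore mainly exit during Induction or Rest.

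Finally, the synopsis says who will be analysed and does not forbid reporting others; the word *only* is not there. That is fair, but no other sensitization set is visible, so completers alone is the natural reading.

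**Conclusion.** The point holds in a limited form. The plan states a completer rule for a primary objective and lets the measured reaction be a reason for leaving. As visible, the two together can leave suspected reactors outside the sensitization result, and any resulting error runs in one direction. This is a feature of a stated rule, which is more than missing detail.

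Its size is unknown: 0 to about 7 of 57 subjects if the completion target is just met. A reader might take 12.3% as the bias. It is the all-cause allowance for leaving, and nothing in the documents says what share would be reaction-related. The 7.1% limit for 0/50 likewise describes completers under an assumed zero and says nothing about those who left.

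The conclusion assumes that the unseen procedure text does not already bring reaction-related withdrawals into the sensitization result. It also allows that an Induction reaction may be irritant, so such a subject is unconfirmed and should not be counted as a proven case.

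**What to change.** Amend the analysis-set sentence in the synopsis in three respects:

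- Keep Challenge completers as the main set for sensitization, and also show any available Challenge readings from subjects who did not finish.
- List beside the sensitization result, as *unconfirmed, Challenge not completed*, every subject withdrawn or stopped for a test-site reaction to the test material who does not complete Challenge. The criterion is an erythema or additional-reaction score of 2 to 4 judged possibly or probably related. Give the scores and the number of patches received.
- Require any statement of no sensitization to refer to that line.

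If the procedure text already contains a rule for reactors, cite it in the same sentence.

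The cost is one amended sentence and one extra line in the results. Scores, relatedness and withdrawal reasons are already to be recorded, so no visit or procedure is added, and decisions to stop patching stay with the investigator. In the illustration above, the main result stays at 0/50. The downside is that the line may include irritant reactions, which is why it must carry the unconfirmed label and stay separate from the main count.

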4.1 Identification

The Sponsor's coded test material will be uniquely identified by a CPT trial number. CPT will record the test material name, physical description, lot number (if applicable), Sponsor and date received into the log-in database.

4.2 Storage

4.3 Controls

4.4 Disposition

At the conclusion of the trial, all remaining test material will be retained by CPT for 30 days and then discarded in accordance with local, state and federal laws and regulations unless the Sponsor has arranged for a different disposition in writing.

5 Selection and Withdrawal of Subjects

5.1 Number of Subjects

At least 50 subjects will complete the trial. Subjects who meet all of the inclusion criteria (Section 5.2) and none of the exclusion criteria (Section 5.3) will qualify for the trial.

Protocol: Revision Date: 2/13/18

Page:

NNAU01-001

10 of 21

5.2 Inclusion Criteria

1. Subjects must be 18-79 years of age (inclusive);

- 2. Subjects must understand and execute an Informed Consent Form that includes a HIPAA statement;
- 3. Subjects must be considered dependable and able to follow directions; and
- 4. Subjects must receive a copy of their executed Informed Consent Form.

5.3 Exclusion Criteria

- 1. Subjects who are in ill health, i.e., a febrile illness lasting more than 24 hours in the six days prior to first patch application;
- 2. Subjects who are taking medications other than birth control, which could influence the purpose, integrity or outcome of the trial;
- 3. Female subjects who are pregnant, planning to become pregnant or lactating during the course of the trial;

- 9. Subjects with a significant past medical history of hepatic, renal, cardiac, pulmonary, digestive, hematological, neurological, locomotor or psychiatric disease;
- 10. Subject with a history of asthma only if requiring regular medication or hay fever that required prescription treatment in two or more of the previous three years;
- 11. Subjects with a history of multiple drug hypersensitivity;
- 12. Subjects with immunization less than 10 days prior to the test patch application;
- 13. Subjects with a medical history indicating atopy;
- 14. Subjects with a sensitization or questionable sensitization in a RIPT.

Protocol:

Page:

NNAU01-001 Revision Date: 2/13/18 11 of 21

5.4 Prohibitions and Restrictions

1. No use of aspirin, excluding a daily dose of 81 mg, or non-steroidal antiinflammatory drugs for the duration of the trial:

- 2. No use of tanning beds or sun lamps or deliberate exposure of the test sites to natural sunlight for the duration of the trial;
- 3. No immunization during the trial.

5.4 Withdrawal of Subjects

The subject is free to withdraw their consent to participate in the trial at any time and for any reason, in accordance with the principles of the World Medical Association Declaration of Helsinki (as amended) and of the Belmont Report. The PI also has the right to withdraw a subject from the trial for safety, lack of efficacy or administrative reasons.

Possible reasons why a subject may be withdrawn from the trial include the following:

- 1. Experiences a serious or intolerable AE;
- 2. Develops, during the course of the trial, symptoms or conditions listed in the exclusion criteria, including pregnancy;
- 3. Takes medications that are contraindicated, as described in the exclusion criteria;
- 4. Incurs a protocol violation such as failure to comply with the specified treatment regimen or failure to comply with the visit schedule; or
- 5. Requests an early discontinuation due to:
 - A clinical reaction for which the PI did not consider removal from the trial to be necessary;
 - Other (non-specific) subject-initiated reason

5.5 Disposition of Withdrawn Subjects

The date the subject is withdrawn from the trial and the reason for discontinuation will be recorded on the CRF. All evaluations scheduled for the final trial visit will be completed as soon as possible after the subject is withdrawn from the trial.

When a subject fails to return for scheduled trial visits, the PI or designee will make a reasonable effort to contact the subject and determine why the subject failed to return. This information will be recorded on the CRFs. The PI will encourage all subjects who decide to withdraw from the trial to complete all evaluations, which may be necessary to assure that the subject is free of untoward effects, and to seek appropriate follow-up for any continuing problem.

Methodology

Page: 12 of 21

6.1 Design

[figure not shown]
This is a single-center RIPT in healthy male and female subjects aged 18 to 79 years, inclusive. Subjects will be screened for eligibility within 7 days prior to the first dose administration. Subjects will be asked to appear at the Testing Facility on Day 0 for the first application of patches. During the Induction Phase subjects will be patched 9 times in 21 days. Evaluations of the test sites will occur prior to patch application. The scores of these evaluations will be analyzed for irritant contact dermatitis potential.

After an approximately 2 week Rest Phase, subjects will return to the Testing Facility for the Challenge Phase. Virgin sites on the subjects' back will receive patches. The patches will remain on the test sites for two days of continuous skin contact. Evaluations of the sites will occur the day of patch removal and 1 day and 2 days after patch removal. The scores of these evaluations will be analyzed for allergic contact sensitization potential.

6.2 Patch

Prior to the initiation of the trial, the test material will be supplied as an 8mm disc packaged **6.3 Test Procedure**

Page: 13 of 21

6.3.2 Challenge Phase

6.3.3 Re-Challenge Phase

[figure not shown]
In the event of a significant reaction occurring during the Challenge phase, the PI may decide to schedule a Re-Challenge Patch test for confirmatory purposes. This follow-up investigation will be conducted approximately 2 weeks after the completion of the Challenge Phase. The application of the patch to a virgin test site on the back will be identical to the Challenge Phase. Additionally, the subject may conduct repetitive applications to the anti-cubital fossa for 4 consecutive days. Observations of both test sites will be recorded Days 1, 2 and 3 post application.

Page: 14 of 21

6.4 Evaluation

[figure not shown]
6.4.1 ESS

Erythema at the test site is evaluated according to the ESS shown below. Any score of 2 through 4 will be captured as an AE.

6.4.2 Additional Reaction Scoring

If present, each additional reaction sequela is evaluated according to the following letter scale and a corresponding numerical scale to indicate severity shown below. Any Severity Score of 2 through 4 will be captured as an AE.

7 Statistical Methods

None anticipated.

8 Safety

An adverse event (AE) is any unfavorable and unintended sign, symptom, or disease that may or may not be considered related to the test material. This includes unfavorable or unintended change in body structure (signs), body function (symptoms), abnormal or severely altered laboratory result, or worsening of any pre-existing condition that occurs during the course of the trial.

Page: 15 of 21

Also, each subject will be carefully monitored for the development of any AEs. This information may be obtained from signs and symptoms detected during each examination, observations by the trial personnel or spontaneous reports from the subjects. This includes AEs resulting from concurrent illnesses, reactions to concomitant medications or progressive disease states.

All AEs, whether volunteered, elicited or noted during examination, shall be recorded on the subject's CRF using the Common Terminology Criteria for Adverse Events (CTCAE) v.4.

The PI will evaluate all AEs for their relationship to, or association with the test material (or other causes) and their intensity. Additionally, the actions taken (*e.g.*, reduction of test material concentration, discontinuation of test material application, administration of treatment, *etc.*) and the resulting outcome of the AE will be indicated on a CRF (*e.g.*, Sponsor, CPT, MedWatch or other appropriate Form).

Any subject who is withdrawn from the trial due to an AE will be followed until the outcome of the event is determined, and the PI will prepare a written summary of the event and document the available follow-up information on a CRF.

8.1 Relationship to Test Materials

The relationship or association of the AE to a test material will be characterized as unlikely, possible or probable (Reference 12.3). Assessments shall be recorded on the CRF.

Causality Term	Assessment Criteria
Probable	Event or laboratory test abnormality, with plausible time relationship to test material intake
	Unlikely to be attributed to condition (or disease) or other products in use by subject
	Response to withdrawal clinically reasonable
	Rechallenge satisfactory or not required
Possible	Event or laboratory test abnormality, with reasonable time relationship to test material intake
	Could also be explained by condition (or disease) or other products in use by subject
	Response to withdrawal unclear or lacking
Unlikely	Event or laboratory test abnormality, with a time to test material intake that makes a relationship improbable (but not impossible)
	Condition (or disease) or other products provide plausible explanations

For safety analyses, AEs that are classified as a possible or probable association to a test material shall be considered test material-related AEs.

Follow-up of the AE, after the date of discontinuation of exposure to test material is required if the AE or its sequelae persist. Follow-up is required until the event or its sequelae resolve or stabilize at a level acceptable to the PI and to the Medical Monitor.

16 of 21

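### Could reactions to the SLS positive control end up counted as test material-related adverse events under section 8.1?

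*Combined protocol and SAP*

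**What the plan says.** The Synopsis (Methodology) lists three patch sites per subject: test material, saline, and 0.4% SLS as positive control. The controls are worn alongside the test material in Induction and are not applied at Challenge.

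On capture of events, section 6.4.1 states for erythema: "Any score of 2 through 4 will be captured as an AE". Section 6.4.2 has the parallel rule for other skin reactions: "Any Severity Score of 2 through 4 will be captured as an AE". Neither sentence separates the product site from the control sites.

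Section 8 opens its definition with "An adverse event (AE) is any unfavorable and unintended sign, symptom, or disease". It also asks the investigator to judge each event against the test material and against other possible causes.

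Section 8.1 offers three ratings: *Probable*, *Possible* and *Unlikely*. The criteria concern timing, alternative explanations, response to withdrawal and rechallenge. The pooling rule is: "For safety analyses, AEs that are classified as a possible or probable association to a test material shall be considered test material-related AEs".

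The Synopsis (Statistical Methods) plans to tabulate the skin scores and summarise event incidence, and to summarise maximum intensity and duration by treatment group. Section 7 plans no statistical methods.

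**The concern.** A positive control is there to provoke a reaction, so scores of 2 or more at the SLS site are foreseeable and the plan makes each one an adverse event. Section 8.1 rates every event against the test material, has no category for unrelated events, and takes no account of the patch under which the reaction appeared. Because the three patches are worn together, timing cannot tell an SLS reaction from a product reaction. If *Possible* is the closest literal fit, the pooling rule carries it into the test material-related total. A product that caused no reaction at all could then be reported with related events produced by the irritant control.

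The Synopsis does not obviously prevent this. Its incidence sentence gives no breakdown by site, and treatment group is not defined for a design in which every subject receives all three materials.

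**Working it through.** The plan gives no figure on this point to reproduce, so the main check is a reading of the table for one case: a score of 2 to 4 at the SLS site during Induction. The SLS patch is taken to be another product in use by the subject.

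| Row in 8.1 | Criterion | SLS-site reaction |
|---|---|---|
| *Probable* | plausible timing | met |
| *Probable* | another product is not a likely cause | not met; the SLS patch is the obvious cause |
| *Possible* | reasonable timing | met |
| *Possible* | "Could also be explained by condition (or disease) or other products in use by subject" | met in form |
| *Possible* | "Response to withdrawal unclear or lacking" | arguable; removing all patches together does not separate them |
| *Unlikely* | timing makes a link improbable | not met on timing alone |
| *Unlikely* | "Condition (or disease) or other products provide plausible explanations" | met |

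Counting ticks, *Possible* has two criteria met and one arguable, against one of two for *Unlikely*. But the table does not say that every criterion in a row must hold, or that the row with most ticks wins. The two alternative-cause criteria also differ in force. The *Possible* wording suits an event with two live candidate causes. The *Unlikely* wording suits an event that something else explains. A reaction confined to the skin under an SLS patch is the second kind. With the section 8 instruction to weigh other causes, *Unlikely* is open to the investigator and is the natural choice.

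**Is the AE definition in conflict with 6.4?** The opening of section 8 joins its two adjectives with *and*, which seems to exclude an intended control reaction. The next sentence, on changes in signs and symptoms, joins them with *or*, and the Definitions section calls an AE any negative experience. An unfavourable reaction at the SLS site is therefore an AE under section 8 as well as under 6.4. There is no contradiction.

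**Size if the table were applied mechanically.** Let s be the share of subjects with an SLS-site score of 2 or more, and m the share of those whom the investigator rates *Possible*. Then r = s × m is the share of subjects wrongly counted. The documents give neither s nor m, so the values below are assumptions. With n = 57 planned subjects:

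- Expected number wrongly counted = 57r. Chance of at least one = 1 − (1 − r)^57.
- r = 0: 0 subjects, 0%.
- r = 1%: 57 × 0.01 = 0.57 subjects; 1 − 0.99^57 = 43.6%.
- r = 5%: 2.85 subjects; 1 − 0.95^57 = 94.6%.
- r = 10%: 5.7 subjects; 1 − 0.90^57 = 99.8%.

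Exact (Clopper-Pearson) 95% intervals: 0/57 gives 0 to 6.27%; 1/57 = 1.75% gives 0.04 to 9.39%; 3/57 = 5.26% gives 1.10 to 14.62%.

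At the extreme of m = 1, SLS reaction rates of 10%, 30%, 50% and 80% give 5.7, 17.1, 28.5 and 45.6 subjects. With the investigator judging by site, m = 0 and the count is 0 whatever s is. The result depends on m, which the documents leave to a clinician who can see which patch caused the reaction.

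**What the count feeds.** Patch-site events are the skin scores of 2 to 4, which the Synopsis already tabulates and which are read site by site. A wrong label would not hide where a reaction occurred. In the visible text, no hypothesis, threshold or stopping rule uses the related-event total. The aggregate-event criterion for notifying the IRB in section 8.3 requires a finding that the problem was unanticipated, which reactions to a deliberate irritant are not.

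**The case for a change.** The best case for a change is that a written table should not need common sense to give the right answer. To rate an SLS reaction *Unlikely*, the investigator has to pass over the timing criterion in that row, and nothing legible in section 8.1 tells them to. The summary by treatment group covers intensity and duration rather than incidence, and would not alter the related flag in any case. A sentence on site would cost almost nothing.

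Part of this stands. The visible text has no attribution rule for control sites, timing cannot discriminate during Induction, and a strictly literal rater could reach *Possible*.

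Three things weaken it. First, the protocol does not mandate that rating. Second, treatment group can sensibly mean only the material worn in this design, so an analyst would split the event tables that way. Third, section 4.3 on controls, the section 6.3 procedures and both scoring tables are missing from the text available for review, so control handling may be specified there.

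Reading SLS as itself a test material, which would push the rating to *Probable*, runs against the protocol's consistent separation of the test material from its two controls. A rigid rule that only product-site reactions may count would also remove judgement that section 8 gives the investigator.

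**Conclusion.** No change to the plan is needed. Section 8.1 is silent on control-site events, but sections 8 and 8.1 together let the investigator rate an SLS reaction as unlikely to be due to the test material, and anyone who can see the patch would do so. If that judgement failed, each affected subject would add 1/57 = 1.8 percentage points (1/50 = 2.0 among the minimum number of completers) to related-event incidence. The chance of at least one runs from 0% to 99.8% as r goes from 0 to 10%, a range set entirely by assumed inputs and so no evidence that the error would occur. The irritation and sensitization conclusions do not use this count.

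This rests on two assumptions: that the investigator takes account of the site when judging cause, and that the event tables are split by material, as the treatment-group wording implies. Both are ordinary practice in a patch test with three sites per subject.
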